### 1.5.2 CAB LA

Through October 2018, approximately 4236 adult participants have been exposed to at least one dose of CAB (oral and/or LA) across 18 completed or ongoing Phase 1, 2 & 3 clinical trials (see Table 1.1).

**Table 1.1 Cumulative CAB Exposures from Phase 1 through Phase 3 Clinical Studies Through October 2018**

Treatment Population/ Dose	Duration	Completed	Ongoing/ Concluded a	Total
Healthy Volunteers/HIV-Uninfected				
5 to 150 mg oral	Single dose	208	0	208
10 to 30 mg once daily oral	10 to 28 days	293	1694	1987
150 mg every 12 hours oral	3 doses	40	0	40
100 – 800 mg IM/SC LA	Max 763 days g	230 b	1377 c	1607
Any dose		599	1694	2293
HIV-infected patients				
5 to 30 mg once daily oral (Ph 2a)	10 days	15	0	15

10 to 60 mg once daily oral (Ph 2b)	Max 2247 days h	0	181	181
30 mg once daily oral (Ph 2b)		0	1739	1739
Up to 800 mg IM LA d	Max 1477 days g	0	1745 e	1745
Any dose		15	1928	1943
All participants				
Single dose oral (5 to 150 mg)		208	0	208
Repeat dose once daily oral (5 to 60 mg)		308	3614	3922
150 mg oral every 12 hours x 3		40	0	40
Single or repeat dose LA injection (100 to 800 mg)		230 b	3122 f	3352
Any dose		614	3622	4236

a. Concluded studies: study completed through follow-up; and/or clinical study report is in preparation

b. 172 participants received both oral and LA dosing

c. All participants received both oral and LA dosing

d. Includes 400 mg Q4W and 600 mg Q8W dosing

e. 1736 participants received both oral and LA dosing

f. 3113 participants received both oral and LA dosing

[figure not shown]
g. Detectable CAB concentrations can remain for up to 72 weeks following the last CAB injection

h. As of 28 Dec 2014, all participants had transitioned to CAB 30 mg in the Open-Label phase of study LAI116482 (LATTE-1), therefore, the longer durations apply to the 30 mg dose only

The regimen proposed for this study was evaluated in HPTN 077 Cohort 2. For the HPTN 077 study, participants were low-risk HIV-uninfected individuals at eight sites globally, randomized (3:1) to daily oral CAB 30mg (or placebo) for four weeks, followed by CAB (or PBO) 800mg IM at weeks 5, 17, and 29 (Cohort 1) or 600 mg IM at weeks 5, 9, 17, 25, and 33 (Cohort 2). One hundred ten participants enrolled in Cohort 1, 89 in Cohort 2. Ninety-four percent of participants completed the oral phase, 89% received at least one injection, and 75% completed all injections, which did not differ by arm, cohort or sex. Over 41 weeks, injection site pain and injection site reactions (ISR) were more common in CAB vs. placebo. No other differences were found in safety or tolerability. ISR led to injection discontinuation in 2/134 (1.5%). Cohort 2 dosing consistently achieved plasma trough targets whereas Cohort 1 dosing did not. Overall, CAB was well tolerated among low-risk HIV-uninfected men and women.

In HPTN 077, overall 65% of the study participants were female. Median BMI was 28 kg/m^2 in female participants and 25 kg/m^2 in male participants. Among participants in Cohort 1 (who received a split injection of CAB-LA 800mg IM q12 weeks), males had a higher geometric mean Cmax after the first injection, but significantly lower trough concentrations than female participants after all three injections. Trough CAB levels were below 4X PA-IC90 in 72%, 35%, and 32% of male participants at weeks 17, 29, and 41, respectively. In contrast, trough CAB levels in female participants were largely at goal throughout the trial, with 24%, 5% and 0% of female participants having trough levels below 4X PA-IC90 at weeks 17, 29, and 41. In Cohort 2 (Figure 1.1) (CAB LA 600mg IM q 8 weeks), male participants achieved significantly higher CAB Cmax, AUC0-tau, and Ctrough after the first injection than female participants (and overall, participants with lower BMI were observed to have significantly higher trough concentrations after the first injection). However, CAB trough levels < 4X PA-IC90 (between 1 and 4X the PA-IC90) were observed in 5%, 20%, 20%, 16%, and 11% of male participants after injections 1, 2, 3, 4, and 5, respectively. For female participants, 21%, 5%, 3%, 0%, and 3% had CAB trough levels below 4X PA-IC90 after injections 1, 2, 3, 4, and 5, respectively.

**Figure 1.1: CAB LA PK Profiles following Q8W Dosing in Males and Females (HPTN077, Cohort 2)**

During the 76-week follow-up phase of the HPTN 077 study, differences were observed in the median time to undetectable cabotegravir concentrations between men and women: 42.7 weeks (range 20.4-134) in men as compared to 66.3 weeks (range 17.7-182) in women. CAB was detectable in plasma in 22% of men and 63% of women at 60 weeks and in 13% of men and 44% of women at 76 weeks post the last injection). The observed PK in HPTN 077 supported the development of CAB for HIV prevention using 600mg IM every 8 weeks with a 4-week loading dose for all sexes.

## 1.6 Genital Tract (GT) Tissue Levels after Oral and Injectable Administration

Genital tissue concentrations have been measured after CAB LA 400 mg IM single dose administration in 24 healthy men and 15 healthy women. Median cervical and vaginal tissue concentrations ranged from 16-28% (overall range 0-70%) of plasma concentrations, roughly 1 x PA-IC90 (0.166  $\mu$ g/mL). Median rectal tissue concentrations were  $\leq$  8% of plasma concentrations (range 0-20%). Further tissue studies using single and multiple doses of the 800 mg IM dose are currently ongoing.

## 1.7 Pediatric Dosing

Currently, there is no previous clinical trial experience with oral CAB or CAB LA in humans under 18 years of age. This protocol will enroll using a weight-based approach rather than age based. This allows for an eventual adolescent indication for LA CAB in adolescents at-risk, regardless of age. The supplemental adolescent indication for Truvada® was entirely weight-based (down to 35 kg) for adolescents at risk of HIV. Also, by not specifying a lower limit of age, this allows sites the flexibility to enroll participants that meet the behavioral and physical criteria necessary to qualify. Each site will have ethics review and will consider these criteria in light of community standards; and each investigator of record will be able to determine whether a candidate is appropriate for enrollment or not. These

decisions will then be made with consideration for the local context of each site/community, rather than arbitrarily choosing what age should be the lower limit.

### 1.7.1 Preliminary Results MOCHA (IMPAACT 2017)

The IMPAACT 2017 trial began enrolling in April 2019. IMPAACT 2017 (NCT03497676) is a Phase I/II, multi-center, open-label, non-comparative study to confirm the dose and evaluate the safety, tolerability, acceptability, and PK of oral CAB, long-acting injectable CAB (CAB LA), and long-acting injectable RPV (RPV LA) administered monthly among up to 155 virologically suppressed HIV-1 infected children and adolescents aged 12 to <18.

As of January 2020, 7 adolescent HIV infected participants in IMPAACT 2017 (MOCHA) aged 12 to 17 years (40 to <50kg: n=4, >50 kg: n=3) had PK collected and analyzed following oral CAB 30 mg once daily and three injections of the CAB LA adult monthly regimen (600 mg IM initiation injection, followed by two monthly 400 mg IM injections). Median (range) CAB PK parameters were within the desired target ranges, specifically Week 2 oral AUC 167.0 (131.1-326.8)  $\mu\text{g}\cdot\text{h}/\text{mL}$  and Week 16 IM trough 2.9 (1.2-6.2)  $\mu\text{g}/\text{mL}$ , and were similar to adult exposures (Table 1.2).

**Table 1.2: Pharmacokinetic Parameters following Cabotegravir Orally Once Daily and Initiation and Monthly Continuation Intramuscular Injections in Adults**

Dosing Phase	Dosage Regimen	Geometric Mean (5 th , 95 th Percentile) a	
		AUC (0-tau)b (mcg $\cdot$ h/mL)	C taub (mcg/mL)
Oral Lead-In c	30 mg once daily	145 (93.5, 224)	4.6 (2.8, 7.5)
Initial Injection d	600 mg IM Initial Dose	1,591 (714, 3,245)	1.5 (0.65, 2.9)
Monthly Injection e	400 mg IM monthly	2,415 (1,494, 3,645)	2.8 (1.7, 4.6)

a All pharmacokinetic parameter values based on pooled FLAIR and ATLAS individual post-hoc estimates from cabotegravir population pharmacokinetic model (n = 581, 2018N384611\_01).

b tau is dosing interval: 24 hours for oral administration; 1 month for IM injections of extended-release injectable suspension.

c Oral lead-in pharmacokinetic parameter values represent steady-state.

[figure not shown]
d Initial injection AUC(0-tau) value includes contribution following oral dosing because the initial injection was administered on the same day as the last oral dose; however, the Ctau value at Week 4 reflects the initial injection.

e Monthly pharmacokinetic parameter values represent Week 48 data.

Preliminary CAB data observed in adolescent participants were compared to *a priori* predictions in adolescents from population PK (POP PK) modelling and simulation (Figure 1.2). The CAB POP PK model was developed utilizing exposure data from adult participants (n=1647) in clinical studies with efficacious dosing regimens having an acceptable safety profile with Q4W and Q8W injections, and simulations were conducted taking into account any potential age and weight related impact on PK, to recommend appropriate doses in adolescents that achieve comparable exposures to those seen in adults. The preliminary adolescent PK data are in

agreement with the predicted exposure range and within thresholds (Figure 1.2). Given the strong agreement of observed data with predictions, the model is considered suitable to predict exposure in adolescents  $\geq 35$  kg for any dosing regimen. Predicted exposures following CAB LA Q8W administration in adolescents are shown in Table 1.2.

**Figure 1.2: Preliminary Observed CAB concentrations in adolescents compared to model predictions based on POP PK analyses from adult studies (IMPAACT 2017 Cohort 1C)**

Note: The plots represent the CAB systemic exposure: solid line and shaded band reflect the population pharmacokinetic model predictions (median and 90% interval); the dots represent the observed individual subject data. The dashed lines represent the maximum observed geometric mean exposure from the TQT study at (22.5  $\mu$ g/mL) at supratherapeutic doses following 150 mg q12h x 3 and the target threshold concentrations at trough (0.65  $\mu$ g/mL).

**Table 1.3: Predicted Steady State CAB Parameters following CAB LA IM Q8W regimen compared with Observed and Estimated data in Adults**

		Predicted $C\tau$ ( $\mu\text{g/mL}$ ) b	
		Post First Injection	Post Second Injection c
Adolescent Body weight	35 to <50kg	2.49 [0.98, 4.72]	2.34 [0.84, 3.98]
	$\geq 50\text{kg}$	1.76 [0.69, 3.49]	1.76 [0.77, 3.05]
Observed adult data		1.50 [0.65, 2.90] a	1.61 [0.80, 2.99] d

a. Geometric mean [5th and 95th percentile] - Week 8 pre-dose concentrations were obtained following a CAB 600 mg IM dose.)  
 b. Median [90% prediction Interval]  
 c.  $C\tau$  after second injection is 8 weeks post injection  
 d. Geometric mean [5th and 95th percentile] -  $C\tau$  at Week 48 with Q8W dosing regimen (ATLAS 2M, 207966)

### 1.7.2 Results from HPTN 077

A population PK model (n=1647) that included data from HPTN 077 (n=134, 89 females, 45 males) and 15 other studies was used to predict exposures following the proposed CAB LA Q8W regimen in adolescents. Gender and BMI are significant covariates affecting the absorption rate following IM administration and were retained in the model to extrapolate to smaller adolescent males expected to enroll in HPTN 083-01. Model predicted concentrations in adolescent males (simulated with median weight and BMI of 63 kg and 21 kg/m^2, respectively) to enroll in HPTN 083-01 are similar to adult males in HPTN 077 (median weight and BMI of 77kg and 24 kg/m^2, respectively) receiving the same regimen and below oral dosing, and therefore are expected to be safe in this population (Table 1.4). Approximately 95% of male subjects are expected to achieve trough concentrations > 4x PA-IC90 following the 5th injection. This regimen is currently being evaluated in uninfected adult males and females in HPTN 083 and HPTN 084, respectively, and has maintained HIV suppression in infected adults when combined with RPV LA (LATTE-2).

**Table 1.4: Predicted CAB Parameters following Injection 5 of the CAB LA 600mg IM Q8W Regimen in Male Adolescents compared with Predicted and Observed Data in Male Adults in HPTN 077**

Plasma CAB Parameter (( $\mu$ g/mL))	Male Participants in HPTN 077 Median (range)		Predicted Exposures Male Adolescents $\geq 50$ kg (110 lbs.)		
	Predicted Parameters 30 mg Once Daily	Observed Data 600mg IM Q8W (Injection 5)	Median (90% PI)	Peds:Adults Relative Exposure	
				Vs 30mg	Vs 600mg
Oral Cmax or C,Wk 34 (1-week post Inj5)	7.6 (4.6 - 12.0)	3.4 (1.6 - 12.9)	5.0 (2.7, 9.1)	0.7	1.5
Oral C $\tau$ or C,Wk 41 (8-weeks post Inj5)	4.5 (2.3 - 7.6)	1.78 (0.50 - 4.2)	1.8 (0.5, 3.4)	0.4	1.0

Plasma CAB will be evaluated during follow up period and but is not expected to be detectable in a majority of subjects one year after the final injection.

Based on adult dosing data and pharmacokinetic modeling, oral CAB 30mg and CAB LA 600mg IM are expected to be safe in adolescents and have been selected as the initial regimen for the IMPAACT 2017 study - the same as the adult CAB regimen in current Phase III studies. While somewhat higher CAB plasma concentrations are expected in lower weight adolescent participants, the safety and tolerability seen in adults at the higher oral CAB dose of 60 mg daily and CAB LA dose of 800mg q 8 weeks tempers any safety concerns.

Seven uninfected participants in HPTN 077 weighing  $<50$ kg at baseline received CAB LA injections during the study. Individual W41 C $\tau$  values following final injections in participants  $<50$  kg ranged from 0.616  $\mu$ g/mL to 4.17  $\mu$ g/mL (Table 1.3), which is within the range of W41 C $\tau$  for the study population overall of 0.203 to 4.72  $\mu$ g/mL for Cohort 1 (n=57) and 0.503 to 4.62  $\mu$ g/mL for Cohort 2 (n=52) and are consistent with expected concentration targets. Individual t1/2 estimates ranged from 13.6 days to 90.4 days in participants  $<50$  kg and from 19.8 to 183 days in Cohort 1 overall and from 13.6 to 241 days in Cohort 2 overall.

## 1.9 Weight gain

There is emerging evidence from randomized trials that the use of integrase inhibitors could lead to significant increases in body weight. Two trials of raltegravir and three involving dolutegravir all observed greater weight gain increases in integrase containing regimens. These effects appear to vary by gender and race, with highest increases observed in women and those of black race. The mechanism for this needs to be fully elucidated. These data are from populations receiving treatment and more data is needed in healthy HIV uninfected populations using PrEP. HPTN 077 evaluated changes in weight and fasting metabolic parameters in 177 HIV-uninfected individuals randomized to cabotegravir or a placebo who had received at least one injection. No differences between study groups were found for change in weight or fasting metabolic parameters overall, or for subgroups. Among the 146 participants with paired weights, between W0 and W41 the median increase in weight for CAB treated participants was 1.1 (IQR -0.9, +3.0) kg compared to median 1.0 (IQR -1.2, +3.2) kg gained by PBO treated participants (=+0.1 kg, p=0.66). The distribution of weight changes across the 41 week treatment period did not

differ between CAB and PBO-treated participants, nor when divided into the oral phase ( $=+0.3$  kg,  $p=0.6$ ) and the injection phase ( $=+0.2$  kg,  $p=0.65$ ). A 5% or greater increase in weight from W0 to W41 was seen in 24 (22%) CAB participants and 7 (18%) of PBO participants ( $p=0.62$ ).

### **1.10 Rationale for use of Oral Run-in Prior to Injectable Dosing**

The CAB LA formulation has a PK decay rate that exposes the injected individual to detectable levels of CAB for a year or more after an injection (see [Section 1.5.2](#) of the protocol). In order to maximally identify any acute toxicity prior to administration of a non-dialyzable, non-removable depot injection, a five-week lead-in period of daily oral (short acting) CAB will be employed. This lead-in period will be evaluated with serial safety assessments prior to injectable administration. The current plans for product labeling should FDA approval be granted include an oral lead-in strategy when adequate safety is established after four weeks of oral drug exposure. The 5-week exposure in this study is designed to provide un-interrupted study product coverage while awaiting return of the Week 4 safety laboratory assessments.

## **2.0 STUDY OBJECTIVES AND DESIGN**

### **2.1 Primary Objectives**

- To evaluate the safety, tolerability and acceptability of CAB LA in healthy, HIV-uninfected male adolescents aged below 18 years.

### **2.2 Secondary Objectives**

- To examine adherence to and timeliness of injections over time among adolescent participants who are provided CAB LA and information regarding its safety and unknown efficacy.
- To examine patterns of sexual risk behavior over time among adolescent participants who are provided CAB LA and information regarding its safety and unknown efficacy.
- To evaluate the safety of CAB LA for 48 weeks of follow-up after final injection.
- To characterize the pharmacokinetics of CAB LA.

### **2.3 Study Design and Overview**

We propose a single arm, open label, safety, tolerability, and acceptability study ( $n=$  approximately 50) in sexually-active, healthy adolescents assigned male sex at birth.

Study participation includes, Step 1: a 5-week oral CAB 30mg QD safety lead-in followed by a series of 5 intramuscular (IM) injections of 3 mL (600 mg), administered at 8-week intervals after a 4-week loading dose (injections at weeks 5, 9, 17, 25 & 33) in Step 2. Adherence support strategies (e.g., counseling, reminders, pill cases) will be included to support pill-taking during the first five weeks and to support retention during the injectable phase. A safety visit will follow each injection to ascertain pharmacokinetic-peak safety data, including injection site reactions. Step 3: a blood draw visit, the +8

Week Visit, will follow the last Step 2 injection to monitor CAB drug levels. All participants who have received at least one injection will be followed for 48 weeks after their last Step 2 injection. Waning levels of cabotegravir (the PK tail) will be covered with locally sourced oral Tenofovir/Emtricitabine (Trade name: TDF/FTC, Truvada®) for daily use for 48 weeks or the participant can opt to continue CAB LA injections for the duration of Step 3. Behavioral and acceptability data will be collected via computer-assisted self-interview (CASI).

Participants who discontinue study product during Step 2 for any reason other than HIV infection or AE occurrence will be transitioned to open label Tenofovir/Emtricitabine (Trade name: TDF/FTC, Truvada®) for 48 weeks.

Finally, in-depth qualitative interviews will be conducted after the end of Step 2 (Week 34) with 10 participants (total, across all sites) to explore issues of acceptability and preference for oral tablets and/or injections. Additionally, up to 10 parents/guardians of participants (total, across all sites) will be asked to participate in in-depth interviews to explore facilitators and barriers to adolescent enrollment in biomedical clinical trials as well as parental acceptability of injectable prevention products for youth.

As previously mentioned, we have chosen an unblinded, single arm trial because it is most developmentally-appropriate for adolescents and minimizes participant and staff burden, while also offering a more streamlined visit schedule than the parent protocols and, hopefully, promoting study drug adherence.

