##### Step 3 – Follow-up Phase

All participants who have received at least one injection will be followed for 48 weeks after their last injection, beginning with a blood draw visit, +8 Week Visit, that will follow eight weeks after the last injection to monitor CAB drug levels. Waning levels of cabotegravir (the PK tail) will be covered with locally sourced oral Tenofovir/Emtricitabine (Trade name: TDF/FTC, Truvada®)) for daily use for 48 weeks. Participants will also have the option to remain on CAB LA injections as one 3 mL (600 mg) IM every 8 weeks for 48 weeks, should they choose..

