## **4.2 Study Product Acquisition and Accountability**

The CAB study products (oral and LA injectable) for Steps 1, 2 and 3 are being provided by ViiV Healthcare. For Step 3, the sites will provide locally sourced Tenofovir/Emtricitabine (Trade name: TDF/FTC, Truvada®) for 48 weeks after the participants' last CAB LA injection.

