#### **5.7 Step 3, Follow-up Phase**

##### **Follow-up Phase**

All participants will be followed for 48 weeks following their last injection in Step 2 (per [Appendix III and IV](#)) and will have the choice of continuing on CAB LA or being provided with Tenofovir/Emtricitabine (Trade Name: TDF/FTC, Truvada®). If participants would like to switch from TDF/FTC to CAB LA in Step 3, that is allowable, but it will not lengthen Step 3.

Step 3 will begin with the +8 Week Visit, in which participants who received the Week 33 injection will return for a blood draw eight weeks afterwards, in order to complete PK monitoring of drug levels of CAB. Participants who do not receive the week 33 injection will have a +8 Week Visit after their last injection visit and continue to be followed per the Step 3 Follow-up Phase.

Both clinical and laboratory evaluations will occur during follow-up phase visits as well as CASI administration for either behavioral or acceptability assessments (see [Appendices III. and IV.: Schedule of Evaluations for Follow-up Phase – Step 3-Oral PrEP and Step 3-Injection](#)).

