### Step 3 – Follow-up Phase

Participants with confirmed HIV infection during Step 3 will not receive oral Tenofovir/Emtricitabine (Trade name: TDF/FTC, Truvada®) or CAB LA and will be followed per the SOE in [Appendix V](#) quarterly through study exit (following an initial +8 Week Visit). In addition, sites will have a standard operating procedure (SOP) that outlines a plan to facilitate immediate initiation of non-study ART and link with appropriate HIV services in the event that a participant becomes HIV-infected during any Step of the study, and in particular during Step 2 of the study, to prevent emergence of drug resistance. Participants who seroconvert will be referred for care; sites will not be responsible for the actual provision/payment of ART. Neither ART nor funds for provision of ART will be provided by the study.

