## **7.0 STATISTICAL CONSIDERATIONS**

### **7.1 Review of Study Design**

This is a single arm, open label, safety, tolerability, and acceptability study of CAB LA for prevention of HIV-acquisition in sexually-active, HIV-uninfected adolescents (below aged 18 years old at time of enrollment).

The study includes a 5-week oral CAB 30mg QD safety lead-in followed by a series of 5 intramuscular (IM) injections of 3 mL (600 mg) CAB LA administered at 8-week intervals after a 4-week loading dose (injections at weeks 5, 9, 17, 25 & 33). Follow up on study product (oral and injectable) will occur for 34 weeks. All participants who have received at least one injection will be followed for 48 weeks after their last injection. Waning levels of cabotegravir (the PK tail) will be covered with locally sourced oral Tenovovir/Emtricitabine (TRADE NAME: TDF/FTC, TRUVADA®) for daily use or continued use of CAB LA for 48 weeks.

The sample size for this study will be set to enroll approximately 50 participants. The sample size for this protocol (n=50) is the number of participants agreed upon by the industry sponsor and regulators in order to provide supplementary safety and behavioral data on adolescents in collaboration with the HPTN 083 and HPTN 084 adult trials. The primary aims of the study are focused on safety, tolerability, and acceptability of this long-acting product.

Finally, in-depth qualitative interviews will be conducted with 10 participants (total, across all sites) after Week 34 to explore issues of acceptability and preference for oral tablets and/or injections. Additionally, up to 10 parents/guardians of participants (total, across all sites) will be asked to participate in in-depth interviews to explore facilitators and barriers to adolescent enrollment in biomedical clinical trials.

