2.1 General Design Considerations

HPTN083-01 is a phase IIB single arm trial designed to establish the minimum safety, tolerability and acceptability data needed to support the use of cabotegravir long-acting injection (CAB LA) in an adolescent population, potentially transforming the field of HIV prevention for young people. The study target population is sexually active, healthy male adolescents aged below 18 years. The study target is to enroll more than 50 participants with at least 50 participants receiving at least one injection. Participant recruitment will take approximately 12 months.

Study participation includes Step 1: a 5-week oral CAB 30mg QD safety lead-in followed by Step 2: a series of 5 intramuscular (IM) injections of 3 mL (600 mg) cabotegravir administered at 8-week intervals after a 4-week loading dose (injections at weeks 5, 9, 17, 25 & 33). Adherence support strategies (e.g., counseling, reminders, pill cases) will be included to support pill-taking during the first five weeks and to support retention during the injectable phase. A safety visit will follow each injection to ascertain pharmacokinetic-peak safety data, including injection site reactions. Step 3: A blood draw visit, the +8 Week Visit, will follow the week 33 injection to monitor CAB drug levels. All participants who have received at least one injection will be followed for 48 weeks after their last injection. Waning levels of cabotegravir (the PK tail) will be covered with locally sourced oral TENOFOVIR/EMTRICITABINE (TRADE NAME: TDF/FTC, TRUVADA®) for daily use for 48 weeks. In Step 3 participants may also choose to continue with 8-week dosing of injectable of CAB-LA for 48 weeks (5 additional injections beyond the initial 5 injections, administered at weeks +8, +16, 24, +32, +40, and +48.) Behavioral and acceptability data will be collected via computer-assisted self-interview (CASI). Total participant commitment for the entire study is up to 87 weeks, or approximately 1.5 years. We anticipate recruitment for the study will take approximately 12 months.

Participants who discontinue study product during Step 2 for any reason other than HIV infection or AE occurrence will be transitioned to open label TDF-FTC for 48 weeks.

There are in total three study sites:

- Adolescent and Young Adult Research at the Core Center (AYAR at CORE), Chicago, IL;
- St. Jude Children's Research Hospital CRS, Memphis, TN;
- Fenway Health CRS, Boston, MA.

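### Protocol 2.3 leaves participants who stop Step 2 injections for an adverse event out of the default move to TDF/FTC, in conflict with the 48-week tail cover stated elsewhere

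*Protocol*

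**What the plan says.** Protocol 2.3 gives the rule for people who stop in Step 2, with 48 weeks of TDF/FTC as the drug: "Participants who discontinue study product during Step 2 for any reason other than HIV infection or AE occurrence will be transitioned to open label". SAP 2.1 repeats it as design background: "any reason other than HIV infection or AE occurrence will be transitioned to open label TDF-FTC for 48 weeks".

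Other sections describe cover for the pharmacokinetic tail more broadly:

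- Protocol 4.1, Step 3, for anyone with at least one injection: "Waning levels of cabotegravir (the PK tail) will be covered with locally sourced oral" TDF/FTC for 48 weeks, with continued CAB LA as an option.
- Protocol 4.2: "For Step 3, the sites will provide locally sourced Tenofovir/Emtricitabine (Trade name: TDF/FTC, Truvada®) for 48 weeks", counted from the last CAB LA injection.
- Protocol 5.7 says of all participants that they "will have the choice of continuing on CAB LA or being provided with" TDF/FTC. It then turns to early stoppers: "Participants who do not receive the week 33 injection will have a +8 Week Visit after their last injection visit", after which they continue in Step 3.
- Protocol 7.1: "Waning levels of cabotegravir (the PK tail) will be covered with locally sourced oral Tenovovir/Emtricitabine", or with continued CAB LA, for 48 weeks.

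The Schema (Study Duration) and the paragraph of 2.3 just before the transition rule say the same. Appendix III lists TDF/FTC provision at +12, +24 and +36 weeks and in its Early Discontinuation column.

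**The concern.** The rule in 2.3 excludes two groups. The HIV exclusion is expected and is repeated where it operates, in Protocol 5.11.2, Step 3: "Participants with confirmed HIV infection during Step 3 will not receive oral Tenofovir/Emtricitabine". The AE exclusion is repeated in no operational section and no reason is given for it. It is also unlimited. Protocol 6.1 defines an AE without requiring a causal link to the product, so the exclusion covers unrelated events and injection site reactions as well as events that would make TDF/FTC unsafe.

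At stake is whether an HIV-negative, at-risk adolescent is supplied PrEP while cabotegravir levels fall. A site working from 2.3 could leave such a participant without supplied drug. A site working from 4.2 and 5.7 would supply it. Protocol 5.8.1 offers referral for oral PrEP on request, which is not supply.

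**Working it through.** The plan states no figure to reproduce here. The check is a comparison of texts, with a small count of supplies and dates.

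**1. Which places state which exception**

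| Place | Who is addressed | HIV exception | AE exception |
|---|---|---|---|
| Protocol 2.3, transition rule; SAP 2.1 | Those who stop in Step 2 | Yes | Yes, any AE |
| Protocol 2.3, preceding paragraph; Schema | Anyone injected at least once | No | No |
| Protocol 4.1, Step 3 | Anyone injected at least once | No | No |
| Protocol 4.2 | Step 3, from last injection | No | No |
| Protocol 5.7 | All, including those without the Week 33 injection | No | No |
| Protocol 7.1 | Anyone injected at least once | No | No |
| Protocol 5.11.2, Step 3 | Confirmed HIV infection | Yes | No |
| Appendix III, provision row | +12, +24, +36, Early Discontinuation | No | No |

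Protocol 5.7 is the most telling row. It deals specifically with people who miss the last Step 2 injection and sends them into Step 3 whatever their reason.

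**2. Does Appendix VI resolve it?** Its Injection Phase paragraph places refusers and AE stoppers on the same quarterly follow-up, yet under 2.3 the refuser moves to TDF/FTC and the AE stopper does not. The ALT, CPK, creatinine clearance and allergy entries speak of stopping study product. The meaning of that term is open:

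- Protocol 4.1 and 4.1.1 list Step 3 TDF/FTC under study product. On that reading, those entries withhold it.
- Protocol 6.2 and 6.2.2 name only oral CAB and CAB LA as study agents, though only for expedited reporting. On that reading, the entries say nothing about TDF/FTC.

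A Step 2 AE arises before the study has given any TDF/FTC. A hold for such an event is therefore most naturally a hold of cabotegravir, but the text does not say so.

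**3. Supplies at stake per person.** Someone who completes Step 2 and chooses oral PrEP has 1 supply at Week 34 (Protocol 5.6) + 3 in Appendix III = 4. A Step 2 stopper normally does not reach the Week 34 supply, so the figure is 3 × 3 months = 9 months. At 12-week spacing these cover weeks +12 to +48 (12 + 3 × 12 = 48). Anything before +12 depends on what the Early Discontinuation column is meant to give.

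**4. Number of people.** SAP 6.4 reports nine enrolled, which is the ceiling. No expected count is derived. The adult stop rates in the protocol are poor proxies: 2/134 in HPTN 077 pools 800 mg and 600 mg cohorts, and 4/94 in ECLAIR is at 800 mg and may describe refusers, whom 2.3 already covers.

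**5. Timing.** Assume the last enrollment was on 31 January 2022 and visits ran on schedule.

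- Last Week 33 injection: 33 × 7 = 231 days later, 19 September 2022.
- Stop after the Week 5 injection: 35 days gives 7 March 2022; a further 48 × 7 = 336 days gives 6 February 2023.
- Completion of Week 33: a further 336 days gives 21 August 2023.

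Step 2 stopping decisions would thus have been over before SAP v2.0 was signed on 17 January 2023, but some tail windows would still have been open.

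**6. Analyses.** No endpoint in SAP sections 8 or 12 turns on this rule. The TDF/FTC Population in SAP 3.1 is defined by who was actually provided the drug, so it stays well defined either way.

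**The case against.** The strongest reply is that 2.3 states a general rule and then a specific exception, and that the specific text governs. Sections 4.1, 4.2, 5.7 and 7.1 omit the HIV exception too, so their silence does not deny an exception stated elsewhere. Protocol 5.7 cannot be taken literally for every AE stopper, since it offers continued CAB LA, which Appendix VI bars after Grade 3 ALT. Grade 3 and 4 injection site reactions and other Grade 3 and 4 AEs already go to the CMC, and a participant with a Grade 1 or 2 AE may continue product, so one who stops anyway may be recorded as having asked to stop. Leaving the remaining cases to individual decision is defensible.

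Much of this stands. It shows that few cases would escape CMC review and that 2.3 may be deliberate for some events. It does not remove the conflict. The HIV exception is carried into the section where it operates and the AE exception is not. If 2.3 does override, the broader statements promise too much and need correcting instead. It would also mean that whether a sore injection site is recorded as an AE or as a refusal decides whether PrEP is supplied by default.

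A reader might go further and infer that 2.3 forbids TDF/FTC after an AE. It does not: it omits these participants from a default, and the CMC's general remit in Appendix VI would allow supply case by case. Nor can one say that Appendix VI is wholly silent, because one fair reading of study product has it withholding TDF/FTC.

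**Conclusion.** The inconsistency is real and minor. The default in Protocol 2.3 and SAP 2.1 excludes all AE stoppers, the rest of the protocol describes tail cover without that exclusion, and Appendix VI can be read either way. Sites could act differently for an HIV-negative AE stopper.

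The size is three Appendix III supplies per person, plus any Early Discontinuation supply, for no more than nine people; how many actually stopped for an AE cannot be told from the documents. A reader might count a full year of four supplies, but that fits completers, not Step 2 stoppers. A reader might also expect some effect on the safety or tolerability estimates; the documents show none.

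Confidence is medium. The conclusion assumes that the Appendix III table was read correctly and that the Study Specific Procedures Manual, which is not available here and to which Protocol 5.0 defers for detailed instructions, does not already settle the matter. The adult male median of 42.7 weeks to undetectable cabotegravir (Protocol 1.5.2) shows why the tail matters, but may not hold for adolescents who stop after one or two injections.

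**What to change.** - **Protocol 2.3:** state that HIV-negative participants who stop Step 2 injections for an AE are offered TDF/FTC for 48 weeks under Appendix III, unless the AE contraindicates it (for example, confirmed creatinine clearance below 60 mL/min) or the CMC advises otherwise.
- **Appendix VI, Injection Phase:** cross-refer to that rule, and state that holding or stopping study product for a cabotegravir-related AE does not by itself bar TDF/FTC.
- **SAP 2.1:** conform the background sentence. No analysis, population or flag changes.

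The drafting is a few sentences, but the process is heavier: a protocol amendment needs IRB and DAIDS approval (Protocol 10.5) and a registration packet (Protocol 10.1). It can be bundled with another amendment. On the dates assumed above it would come too late to change a Step 2 stopping decision, and could affect supply only for anyone whose 48-week tail was still open.
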